2.1.1 General definitions

Study treatment

• Investigational Treatment:

Secukinumab **150 mg** provided in 1.0 mL in PFS for s.c. injection.

Secukinumab **placebo** provided in 1.0 mL in PFS for s.c. injection.

Dates and time windows

Study treatment start and end date

Study treatment start date is defined as the first date when a non-zero dose of study drug is administered and recorded on the Drug Administration Record (DAR) CRF page. Similarly, **study treatment end date** is defined as the last date when a non-zero dose of study drug is administered and recorded on the DAR CRF page of the core study.

Study day

Study day will be calculated as (event date – study drug start date + 1 day) for events that occurred on or after study drug start date (e.g., visit, lab samples, AEs). For events prior to study drug start date (e.g., time of diagnosis), study day will be negative and calculated as (event date – study drug start date). Note that study drug start date is study day 1 and the day before study drug start date is study day -1 (i.e. no study day 0).

Due to the study drug dosing schedule, one month will be considered as 28 days. However, for "time since event" data (e.g., medical history), one month will be considered as 365.25/12 days for events that occurred prior to study Day 1. Time from events prior to the start of study drug, e.g., time since diagnosis, is calculated as the difference between the start date of study drug and the date of prior event.

Note that, the first dose day is Day 1, and the day before the first dose day is counted as Day - 1 (not Day 0).

Baseline and post-baseline definitions

In general, a baseline value refers to the last measurement made prior to administration of the first dose of study treatment. A post-baseline value refers to a measurement taken after the first dose of study treatment.

Treatment Period: There are 2 Treatment Periods for this study defined as:

Treatment Period 1 is defined as the 16-week, placebo-controlled, double-blind Treatment Period starting from baseline till Week 16.

Treatment Period 2 is a 36-week, double-blind active Treatment Period starting from Week 16 till Week 52.

Lost to follow up: The patients whose study completion status is unclear because they fail to appear for study visits without stating an intention to withdraw

On-treatment period: The period where the patients are exposed to the study treatment. For this study the treatment phase consists of 52 weeks.

2.1.2 Visits windows

Visit-windows will be used for the data that is summarized by visit; they are based on the study evaluation schedule and comprise a set of days around the nominal visit day. For any assessment, there are the protocol defined scheduled visits around which visit windows were created to cover the complete range of days within the study. The visit windows are shown in Table 2-1. These apply to measurements taken at every visit. For assessments collected less often, different visit windows will be applied as detailed below.

When visit windows are used, all visits will be re-aligned, i.e., they will be mapped into one of the visit windows. For example, if the *Week 4* visit of a subject is delayed and occurs on Day 46 instead of on Day 29, say, it will be re-aligned to visit window *Week 8*. In the case of major deviations from the visit schedule, or due to unscheduled visits, several assessments of a subject

may fall in a particular visit window (either scheduled or unscheduled). Statistical approaches to handle multiple assessments in a given visit window are specified below.

Of note, subjects are allowed to have gaps in visits.

Analysis Visit	Week	Scheduled Day	Visit Window
Baseline	BSL	1	-28 days to Day 1*
Week 1	1	8	Day 2-11
Week 2	2	15	Day 12-18
Week 3	3	22	Day 19-25
Week 4	4	29	Day 26-43
Week 8	8	57	Day 44-71
Week 12	12	85	Day 72-99
Week 16	16	113	Day 100-127
Week 20	20	141	Day 128-155
Week 24	24	169	Day 156-183
Week 28	28	197	Day 184-211
Week 32	32	225	Day 212-239
Week 36	36	253	Day 240-267
Week 40	40	281	Day 268-295
Week 44	44	309	Day 296-323
Week 48	48	337	Day 324-351
Week 52	52	365	Day 352-379

Table 2-1Assessment windows for scheduled visits

* Baseline measurement before the first drug administration for safety assessments and before the randomization for efficacy assessments. For efficacy, visit windows refer to date of randomization.

2.1.3 Multiple assessments within visit windows

When there are *multiple assessments* in a particular visit window, the following rules are applied to select one value "representing" the subject in summary statistics in a visit window (See Table 2-2).

For baseline assessment definition, see section 2.1.1. For post-baseline visit windows, the following applies (unless otherwise specified):

- for *quantitative variables*, the *closest* to the actual visit is chosen (if two assessments have the same distance, then the earlier one will be chosen);
- for *qualitative variables*, the *worst* record is selected. It is noted that in the analyses performed, *worst* case is always well defined.
- in case qualitative variables are based on quantitative variables, e.g., PASI 75 response, the visit will be assigned to the quantitative variable, and this visit will be used for the derived qualitative variable.

2.2 Analysis sets

The following analysis sets will be used for the statistical reporting and analyses:

Randomized Set: The Randomized Set includes all randomized patients.

Safety Set: The Safety Set includes all patients who received at least one dose of study medication. Patients will be included in the analysis according to treatment received.

Full Analysis Set (FAS): The Full Analysis Set comprises all patients to whom study medication has been assigned. Patients inappropriately randomized (e.g., IRT was called in error for randomization of a screen failed patient) will be excluded from this analysis set.

Psoriasis Subset: The Psoriasis Subset comprises patients in whom at least 3% of body surface area was affected by psoriatic skin involvement at baseline.

Dactylitis Subset: The Dactylitis Subset comprises patients who have LDI >= 1 at baseline.

Up-titrated Subset: Up-titration Subset includes all completed patients who were up-titrated from 150 mg to 300 mg in Treatment Period 2, based on the response.

For efficacy analyses, following the intent-to-treat principle, patients will be analyzed according to the treatment they were assigned to at randomization.

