5.5.9 Discontinuation of study treatment

Study treatment must be discontinued if the investigator determines that continuation of study treatment would result in a significant safety risk for a subject. The following circumstances **require** study treatment discontinuation:

- Withdrawal of informed consent
- Emergence of the following adverse events:
 - a. Any severe or serious adverse event that is not compatible with administration of study medication, including adverse events that require treatment with an unacceptable co-medication
 - b. Onset of lymphoproliferative disease or any malignancy except for treated basal cell carcinoma, treated actinic keratoses, treated in situ carcinoma of the cervix or non-invasive malignant colon polyps which are being or have been removed
 - c. Life-threatening infection
- Any laboratory abnormalities that in the judgment of the investigator are clinically significant and are deemed to place the subject at a safety risk for continuation in the study (A general guidance on clinically notable laboratory values is provided in ([Appendix 1](#))).
- Pregnancy
- Use of any biologic immunomodulating agent except secukinumab (please refer to [section 5.5.8](#) for the other prohibited medications). Any protocol deviation that results in a significant risk to the subject's safety

In addition to these requirements for study treatment discontinuation, the investigator should discontinue study treatment for a given subject if there is a lack of improvement or worsening of their symptoms, or if on balance, he/she thinks that continuation would be detrimental to the subject's well-being.

For any subject whose treatment code has been broken inadvertently for any reason, the appropriate personnel from the site and Novartis will assess whether study treatment should be discontinued.

The investigator must also contact the IRT to register the subject's discontinuation from study treatment.

Patients may voluntarily withdraw from the study for any reason at any time. They may be considered withdrawn if they state an intention to withdraw, fail to return for visits, or become lost to follow-up for any other reason.

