 - Patients who did not meet the responder criteria at Week 16, 28 or 40 will start receiving secukinumab 300 mg every 4 weeks and will continue this dose up to Week 48.
- Patients on placebo (**Group 3**) regardless of their responder status will start receiving secukinumab 300 mg every 4 weeks from Week 16 up to Week 48.

Those patients whose tender and swollen joint counts both reduce by $\ge 20\%$ from baseline will be classified as 'responders' and those patients who do not meet the responder criteria will be classified as 'nonresponders'.

Patients, investigators/site staff, persons performing assessments, and Novartis study personnel will remain blinded to individual treatment assignment from the time of randomization until the final database lock.

Rescue medication will not be allowed during the day of the clinical visit and before

completion of Week 16 assessments. Although no subject will be restricted from receiving necessary rescue medications for lack of benefit or worsening of disease, patients will be discontinued from the study if rescued with prohibited biologics and should obtain end of study assessments at the earliest possible date, provided consent to do so has not been withdrawn.

No stratification at randomization will be performed.

The following figure describes the study design.

Figure 1.1: Study Design

Primary analysis time point

The primary analysis will be performed at Week 16.

Interim analyses

As planned, database lock will be performed at the end of Treatment Period 1 (Week 16), after all patients have completed the Week 16 visit. Data analyses will follow after first database lock.

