Eligible patients will be randomized to secukinumab 300 mg (Group 1), secukinumab 150 mg (Group 2) or placebo (Group 3) for the first 16 weeks (until Week 16 treatment). Note that the treatment groups above for a patient may differ depending on the time period of the analysis and whether one assesses the patient for efficacy or safety.

The analysis will be conducted on all patients' data at Week 16 and at the time the trial ends (Week 52).

For Treatment Period 2, all data analyses will be presented by Weeks 16, 28 and 40, based on the number of patients who switched to secukinumab 300 mg and number of patients who continued in secukinumab 150 mg at the respective visits.

All the assessments from scheduled visits will be included for summaries and analyses, whereas the listing will include available data.

Comparative efficacy data

Comparative efficacy analyses (i.e. inferential efficacy comparisons with placebo) will focus on the time period when both active drug and the placebo are given in a manner suitable for making comparisons (i.e., first 16 weeks of treatment). Comparative efficacy will be performed based on the FAS using the randomized treatment. After week 16 till week 52, the efficacy variables will be summarized descriptively or otherwise specified using inferential analysis, on the FAS.

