2.2.1 Subgroup of interest

Planned subgroups of interest are the subsets defined in Section 2.2.

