2.3.1 Patient disposition

The number and percentage of patients screened will be presented. In addition, the reasons for screen failures will be provided.

The number and percentage of patients in the Randomized Set and FAS who are enrolled, and who completed the treatment periods and who discontinued the study prematurely (including the reason for discontinuation) will be presented at the end of each Treatment Period (Week 16 and Week 52), if appropriate, for each treatment group and all patients.

For each protocol deviation (PD), the number and percentage of patients for whom the PD applies will be tabulated. Type of protocol deviation will also be reported.

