2.7.3 Handling of missing values/censoring/discontinuations

Patients who discontinued prematurely for any reason will be considered non-responders from the time they discontinued. Patients who do not have the required data to compute ACR response (i.e., tender and swollen joint counts and at least three of the five ACR domains) at baseline and at the specific time point will be classified as non-responders. For all other binary variables, non-responder imputation will be applied.

Missing data for continuous variables will be imputed using the last-observation-carried-forward (LOCF) method.

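### SAP 2.2 limits the Up-titrated Subset to completers, which removes switchers who later stop; the effect is minor, and deleting one word cures it

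*SAP*

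**What the plan says.** SAP 2.2 defines the set: "Up-titration Subset includes all completed patients who were up-titrated from 150 mg to 300 mg in Treatment Period 2, based on the response". SAP 2.2.1 adds: "Planned subgroups of interest are the subsets defined in Section 2.2".

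On timing, SAP 1.1 moves to 300 mg those Group 2 "Patients who did not meet the responder criteria at Week 16, 28 or 40". The same section ends Treatment Period 1 just ahead of the Week 16 dose, and SAP 2.1.1 states: "Treatment Period 2 is a 36-week, double-blind active Treatment Period starting from Week 16 till Week 52".

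On completion, the SAP gives no definition. SAP 2.3.1 counts patients "who completed the treatment periods and who discontinued the study prematurely" at Week 16 and again at Week 52. Protocol 5.5.13 treats a patient's participation as complete at Visit 19/Week 52.

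On stopping, Protocol 5.5.9 says that "the investigator should discontinue study treatment for a given subject if there is a lack of improvement or worsening of their symptoms". SAP 2.7.3 then sets the rule for binary outcomes: "Patients who discontinued prematurely for any reason will be considered non-responders from the time they discontinued".

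On the status of later efficacy results, SAP 2.1 states: "After week 16 till week 52, the efficacy variables will be summarized descriptively or otherwise specified using inferential analysis, on the FAS".

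**The concern.** A subset meant to describe patients whose dose was raised should be fixed by what was known when it was raised. Requiring completion makes membership depend on what happens afterwards. A patient who moves to 300 mg, does not improve and stops for that reason would not be counted as a failure. That patient would leave the denominator.

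What is at stake is how the up-titration results are read. Protocol 1.1 and 1.2 present the dose increase in non-responders as a source of information on stronger IL-17A inhibition. A rate computed only on those who lasted to Week 52 could be taken as the benefit among all who switched. The restriction also sits uneasily with the sentence that follows it in SAP 2.2, which invokes the intent-to-treat principle for efficacy.

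**Working it through.** **No planning figure to reproduce.** The documents give no size, dropout rate or response rate for this subset. Their sample size (88 and 44 patients, about 250 randomized) concerns 300 mg versus placebo at Week 16 and plays no part here.

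**Step 1: what *completed* can mean.**
- *Treatment Period 1 completed.* SAP 1.1 closes Period 1 before the Week 16 dose, and the earliest up-titrated dose is the Week 16 dose. Every switcher has passed that point, so the word would exclude nobody.
- *Treatment Period 2 or the study completed.* Protocol 5.5.13 puts this at Visit 19/Week 52. The word then excludes every switcher who stops earlier. This is the only reading with an effect, and the nearest definition in the documents supports it.

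**Step 2: is the exclusion related to outcome?** Protocol 5.5.9 names lack of improvement or worsening as a ground for stopping treatment. Some patients will stop for other reasons, so the direction is a tendency and not a certainty.

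**Step 3: can SAP 2.7.3 repair it?** No. The rule assigns non-response to patients who discontinue, and a completers-only set contains none after the switch.

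**Step 4: size relative to the 2.7.3 rule.** Let N be all switchers, d the share who stop between the switch and Week 52, and R the Week 52 responders. Under 2.7.3 everyone who stops is a non-responder, so all R are completers.
- All-switcher rate = R/N
- Completers-only rate = R/(N(1-d))
- Ratio = 1/(1-d)

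The documents do not give d. The 10% in Protocol 4 and 9.7 is trial-wide loss after randomization, not loss after a switch. Both d and the response rates below are therefore assumptions.

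| Assumed d | Ratio | All-switcher rate 25% becomes | All-switcher rate 40% becomes |
|---|---|---|---|
| 0% | 1/1.00 = 1.00 | 25.0% | 40.0% |
| 5% | 1/0.95 = 1.05 | 26.3% | 42.1% |
| 10% | 1/0.90 = 1.11 | 27.8% | 44.4% |
| 20% | 1/0.80 = 1.25 | 31.3% | 50.0% |

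In counts, with 35 assumed switchers and d = 20%, 7 leave and 28 remain. Fourteen responders are 14/35 = 40% of all switchers but 14/28 = 50% of completers.

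**Step 5: size relative to an observed-data display.** An observed-data Week 52 rate for all switchers already omits those with no Week 52 assessment, so it would lie close to the completers-only rate. The factor in Step 4 is a contrast with the non-responder rule only.

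**Step 6: follow-up after the switch.** SAP 1.1 and Protocol 3.1 and 5.2 place switching at Weeks 16, 28 and 40. Protocol 3.3 describes it as possible at each clinical visit from Week 20 to Week 48 as well. These passages must be reconciled before any follow-up time is quoted. Steps 1 to 4 hold either way, since no version places a switch before Week 16.

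**The case against.** The strongest reply is that the all-switcher result is already planned. SAP 2.4.1 lists a 150-300 mg (NR) efficacy group with no completer limit. SAP 2.5.2 and 2.7.2 summarise ACR20/50/70, Minimal Disease Activity and PASI responses by treatment group and visit to Week 52, with a non-responder-imputed version alongside. A reader who wants stoppers counted as failures will find them there. This stands, and it is the main reason the impact is minor.

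Three further points stand in part.
- *Completed* is not without meaning: the SAP is silent, but Protocol 5.5.13 supplies one. That narrows the point from an undefined term to a choice of population, and it confirms the reading that does the damage.
- No readable analysis names the subset, so whether a response rate will be computed on it is unknown. Section 2.13, cited in the SAP's change table, is not in the public text.
- The listed efficacy objectives are all at Week 16, and the change table records that the set was added after the Week 16 lock.

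A reader might go further and infer that the trial's up-titration findings are inflated by up to 25%, or that failures on 300 mg disappear from the report. The documents support neither. The 25% comes from an assumed dropout rate and applies only against the non-responder rule, and the NR group keeps the patients whom the subset leaves out.

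**Conclusion.** The definition in SAP 2.2 should change. As written, it selects on what happens after the switch, tends to flatter any response rate computed on it, and gives one SAP two populations for the same dose change. The inflation against the 2.7.3 rule is 1/(1-d): nil if nobody stops, and 1.05 to 1.25 for assumed d of 5% to 20%. Against observed data at Week 52 it would be small. This rests on *completed* meaning Week 52, as Protocol 5.5.13 indicates, and on the subset being used for a response rate, which the readable text does not confirm.

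The consequence is confined to interpretation of Treatment Period 2 results. The primary Week 16 test, its significance level and its power are unaffected. It would be wrong to infer that post-Week 16 inference on this subset is planned: SAP 2.1 makes later efficacy descriptive by default, leaves room for inferential analysis, and specifies none for this set in readable text.

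**What to change.** In SAP 2.2, delete *completed*, so that the subset is all Group 2 patients up-titrated from 150 mg to 300 mg in Treatment Period 2 on the basis of response. Keep that last condition, so that responders switched in error are not brought in and the set matches the NR group in 2.4.1. State that 2.7.3 applies to members who stop. If a completers-only display is wanted, keep it and label it supplementary.

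Separately, reconcile Protocol 3.3 with SAP 1.1 and Protocol 3.1 and 5.2 on when non-responders switch.

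Two optional clarifications, not part of the error: say whether observed values or LOCF apply to continuous outcomes after Week 16, since SAP 2.7.2 and 2.7.3 differ; and say that results on this subset are descriptive. Its members have just failed the joint-count rule, so later improvement cannot be separated from regression to the mean or longer treatment.

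The cost is one word deleted and one or two sentences added to the SAP. It needs no new data, no change to treatment and no rerun of the Week 16 analysis.

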2.2.1 Subgroup of interest

Planned subgroups of interest are the subsets defined in Section 2.2.

2.3 Patient disposition, demographics and other baseline characteristics

Summary statistics will be presented for continuous demographic and baseline characteristics and the number and percentage of patients in each category will be presented for categorical variables for each treatment group of all patients, and also by the subgroup of patients with dactylitis at baseline, and the subgroup of patients with enthesitis at baseline. The summaries will be reported for both the Randomized Set and the Full Analysis Set (FAS).

2.3.1 Patient disposition

The number and percentage of patients screened will be presented. In addition, the reasons for screen failures will be provided.

The number and percentage of patients in the Randomized Set and FAS who are enrolled, and who completed the treatment periods and who discontinued the study prematurely (including the reason for discontinuation) will be presented at the end of each Treatment Period (Week 16 and Week 52), if appropriate, for each treatment group and all patients.

For each protocol deviation (PD), the number and percentage of patients for whom the PD applies will be tabulated. Type of protocol deviation will also be reported.

2.3.2 Patient demographic and other baseline characteristics

The following demographic and baseline variables, if collected, will be summarized:

Continuous variables:

- Age (which is derived from date of birth and the screening assessment date)
- Height
- Weight
- Body mass index (BMI) = (body weight in kilograms) / (height in meters)²
- RAPID3

Categorical variables:

- Age categories ($\ge 18 <40$, $\ge 40 <65$, $\ge 65 <75$, 75 years and older)
- Sex
- Race
- Ethnicity
- Child-bearing status (for females only)

Baseline disease characteristics will also be summarized for the following variables:

- The time (years) since first PsA diagnosis, PsA disease duration (if different from time since diagnosis)
- History and, duration of psoriasis, including time (years) since first diagnosis of psoriasis
- Smoking status at baseline
- Alcohol status at baseline
- Tuberculosis (TB) status

2.3.3 Medical history

Any condition entered on the relevant medical history / current medical conditions eCRF will Be coded using the MedDRA dictionary. They will be summarized by system organ class (SOC) and preferred term (PT) of the MedDRA dictionary.

- Summary will be provided for cardiovascular medical history.
- Previous PsA/psoriasis treatments of each therapy will also be summarized.
- Chest X-ray (screening) results will also be listed.

